### **Objectives:**

In this study, we aim to evaluate the gait differences among three different walking modalities with respect to spatiotemporal gait parameters. This will be achieved through a comparative analysis of spatiotemporal data between those groups. To ensure the safety of the subjects, the data collection protocols will be strictly followed, incorporating already tested procedures that have shown no probable risk. The BWSS has been tested with healthy individuals and is manufactured using widely available components in Bangladesh. The objectives of the study are as follows:

- **Study objectives:** To evaluate the variations in spatiotemporal gait parameters of three different walking modalities and analyze and determine which walking technique provides the most reliable gait metrics, suggesting a more stable and possibly advantageous recovery outcome.
- **Study Hypothesis:** We hypothesize that body weight supported treadmill walking will exhibit the least variability in spatiotemporal gait parameters compared to overground walking and self-paced treadmill walking. This suggests that BWST provides a more controlled environment, promoting more consistent and reliable gait patterns, which may translate to a more stable and potentially advantageous recovery outcome for individuals with stroke.

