### Phase-3-Extended Study (0):

The aim of this phase of study is to compare the Spatiotemporal parameter among different waking modalities. The standard protocols will be followed while conducting experiment, in the Department of Biomedical Engineering (BME), BUET. The various aspect of this final and most important component of the study are described below:

**Sample Size calculation:** In this comparative study, the gait velocity in between different waking modalities is considered as the primary parameters. The following formula may use for calculating the sample size for each group of the trial:

$$\text{Sample size, } N = \frac{2\sigma^2(Z_{1-\beta} + Z_{1-\alpha/2})^2}{d^2(k-1)} \quad \dots \dots \dots \quad (i)$$

Where,

N = Required sample size

$d$  = Difference in means of two group (effect size)

$$\sigma = \text{SD}$$

**k** = is the number of groups being compared.

$Z_{1-\beta}$  = It is the desired power

$Z_{1-\alpha/2}$  = Critical value and a standard value for the corresponding level of confidence. (At 95% CI it is 1.96)

To estimate the sample size, we considered the mean difference of the velocity of the post stroke patient to be at least 0.17 with a standard deviation of 0.3. We estimated that 24 individuals would be needed to satisfy the comparative studies between three groups, based on the statistical power of 80%, at a two-sided alpha level of 0.05. The statistical formula (i) used for the comparative test [10]. Considering dropouts and left-against-medical advice (LAMA) cases, sample size  $N = 25$  will be considered. Thus, a total of 25 subjects will be considered for the equal allocation of this study. The different aspects of the study are summarized in Table I.

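### The 80% power stated for the comparison between three groups is power for one pairwise difference in mean gait velocity, and does not cover the claim that one of three modalities is best

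*Protocol*

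**What the plan says.** Under Phase-3-Extended Study, the sample-size calculation takes gait velocity as the parameter for sizing. In formula (i), d is the "Difference in means of two group (effect size" and k "is the number of groups being compared". The inputs are a "mean difference of the velocity of the post stroke patient to be at least 0.17 with a standard deviation of 0.3", and the result is "based on the statistical power of 80%, at a two-sided alpha level of 0.05". The text concludes that "24 individuals would be needed to satisfy the comparative studies between three groups, based on the statistical power of 80" per cent, raises the 24 to 25 for dropouts, and adds that "a total of 25 subjects will be considered for the equal allocation of this study".

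The Objectives section asks which of the three walking techniques gives the most reliable gait metrics. Its hypothesis is that "body weight supported treadmill walking will exhibit the least variability in spatiotemporal gait parameters compared to overground walking and self-paced treadmill walking".

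Table 1 makes gait velocity the primary outcome and has patients walk in all the modalities. Its analysis row lists an unspecified three-group comparison of the primary outcome. The only tests it names, the paired t test and the Wilcoxon signed-rank test, are pairwise.

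**The concern.** The calculation rests on one difference between two conditions, but its power is attached to a comparison of three. The study's conclusion is a superlative: BWST is the least variable of the three. That is true only if BWST is better than overground walking and also better than self-paced treadmill walking. Two contrasts must then succeed together, and the stated 80% does not describe that event.

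There is a second gap. The 80% is for mean velocity, whereas the superlative is about variability. A reader who takes the 80% as the chance of confirming the hypothesis is misled on both counts. A result that is significant against only one comparator could also be reported as confirmation.

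**Working it through.** **Inputs from the protocol** (sample-size calculation): d = 0.17, SD = 0.3, k = 3, two-sided alpha 0.05 (z = 1.960), power 80% (z = 0.8416), N = 24, or 25 with dropouts. The protocol does not say whether 0.3 is the SD in one modality or the SD of the within-patient difference. It gives no correlation between modalities.

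**Step 1: reproduce the stated size.** Formula (i) gives N = 2 × 0.3² × (0.8416 + 1.960)² / (0.17² × 2) = 24.44. The stated 24 is this value rounded down.

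**Step 2: what the formula is.** With k = 3 the factor 2/(k − 1) equals 1. What remains is N = σ²(z + z)²/d², the normal-approximation size for one paired difference whose SD is 0.3. Power for that one contrast is Φ(0.17√N/0.3 − 1.960):
- N = 24: Φ(2.776 − 1.960) = 79.3%
- N = 25: Φ(2.833 − 1.960) = 80.9%

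**Step 3: both contrasts, taking 80% for each at face value.** Assume equal effects and a bivariate normal distribution for the two test statistics. The joint power is the probability that both exceed their critical value:

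| Correlation between contrasts | Joint power |
|---|---|
| 0 | 0.80 × 0.80 = 64.0% |
| 0.25 | 66.1% |
| 0.5 | 68.7% |
| 0.75 | 72.1% |
| 0.9 | 75.0% |

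The value 0.5 follows if variances and correlations are equal across modalities. The two contrasts share BWST, so their covariance is σ²(1 − r) and each has variance 2σ²(1 − r). This is an assumption, not a protocol figure.

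**Step 4: how far the figure moves with other assumptions.** Contrast correlation is 0.5 and N = 25 throughout.
- *Choice of test.* With 0.3 as the SD of differences and 0.17 on both contrasts, joint power is 69.9% by normal approximation and about 65% by paired t test. The single contrast itself falls from 80.9% to 77.6% on that switch, so part of the drop has nothing to do with needing two contrasts.
- *Unequal effects.* If one contrast is 0.17 and the other 0.25 or 0.34 (illustrative values), joint paired-t power is about 77% or 78%, against 77.6% for the single contrast. The gap almost closes.
- *Meaning of 0.3.* If it is a per-modality SD, the SD of differences is 0.3√(2(1 − r)), where r is the within-patient correlation. For r = 0, 0.5, 0.7 and 0.8 this is 0.424, 0.300, 0.232 and 0.190. Joint paired-t power is then about 32%, 65%, 89% and 98%.

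**Step 5: an overall three-group test.** For a repeated-measures F test with equal variances and correlations and an SD of differences of 0.3, power at N = 24 and 25 is 79.9% and 81.7% if one modality differs by 0.17 from two equal ones. It is 67.0% and 69.0% if the three means are evenly spaced over 0.17.

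**Step 6: variability.** None of these figures can be computed for the hypothesis as worded, because the protocol gives neither an effect size nor an SD for any variability measure.

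**The case against.** The strongest objection is that the two statements concern different endpoints. The 80% is for mean velocity, and no section claims a best modality on velocity or attaches 80% to the variability hypothesis. That stands. It rules out any statement about how often this trial would fail to identify the least variable modality. It does not rescue the label, because the 80% is still given for three groups while the calculation handles two.

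A reader might infer that the protocol's own inputs give about 65% joint power, so that one trial in three would miss the best modality. The documents do not support this. That figure requires 0.3 to be the SD of paired differences, exactly 0.17 on both contrasts where the protocol says at least 0.17, an assumed correlation, and a change from the normal approximation to the t test. It also concerns velocity.

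The 80% could instead be read as power for an overall test, since the formula contains k and Table 1 lists a three-group comparison. Step 5 shows that this works when two modalities are equal and fails when the means are evenly spaced. Even a significant overall test would not say which modality is best.

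Finally, rules for declaring a winner are often left to the SAP, which is not at hand. Their absence is therefore not held against the protocol. The point rests on the power label and the hypothesis, both of which are in the protocol's text.

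**Conclusion.** The point holds in a limited form. The stated 80% is power for one pairwise difference in mean gait velocity. It is presented as power for a three-group comparison and does not cover the best-of-three claim, which needs two contrasts and concerns variability. The arithmetic itself reproduces; the fault is in what the figure is said to cover.

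The size of the gap is illustrative. It is about 64% to 75% against 80% if each contrast has 80% power with equal effects and their correlation lies between 0 and 0.9. The gap nearly vanishes if the second difference is clearly larger. The level is far more uncertain, at about 32% to 98% for within-patient correlations 0 to 0.8, if 0.3 is a per-modality SD. The documents fix no single replacement figure.

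**What to change.** In the sample-size calculation:

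1. Relabel the 80% as power for one pairwise contrast in mean gait velocity, and state that it is not the power of the best-of-three claim on variability.
2. State that BWST will be declared least variable only if both of its paired contrasts, against overground and against self-paced treadmill walking, are significant at two-sided 0.05 with BWST less variable in each. Because BWST is named in advance and both contrasts must succeed, this needs no split of alpha.
3. If a joint power is quoted, mark it as illustrative and give its assumptions: 80% per contrast, equal effects, about 64% to 75% for correlations 0 to 0.9. Say whether 0.3 is a per-modality SD or the SD of within-patient differences.

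The cost is a few sentences and a less favourable stated power. No more patients are asked for and no procedure changes.

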**Table 1: Summary of the comparative study between healthy and post stroke individuals**

Aspect of the study	Description
Study Type	Comparative
Design	Comparative study
No of subjects	25
Objective	Evaluate the variations in spatiotemporal gait parameters of those
waking modalities.	
Study Population	Inclusion Criteria for post-stroke patients:

	
 
Participants must be between 18 to 75 years old.
 
More than 1- month post stroke.
 
Participants must be able to walk with or without assistance.
 
Patients including both the male and female.
 
Participants must be able to provide informed consent to participate in the study.
 
 
Exclusion Criteria for post-stroke patients:
 
 
Severe cognitive or communicative disorders.
 
Significant joint malposition.
 
Psychological, cognitive dysfunction, and any other neuromuscular problem.
 
Pregnant women will be excluded to avoid any potential risks to the mother and fetus.
 
Unstable cardiovascular disease
 

Procedure	
Post stroke group:
 
 
Giving instruction
 
Randomly assigning patients to all the modalities
 
Data collection through force plate and video cameras
 
Extracted spatiotemporal parameters from recorded data
 

Outcomes	
Primary Outcome:
 
 
Gait velocity
 
 
Secondary Outcome:
 
 
Step length
 
Stride length
 
Cadence
 
Stance and swing phases duration
 
Single and double support time
 
Ground reaction force
 

Data Collection	
Data collected before trial:
 
 
Patient clinical condition
 
Time after stroke and before data collection
 
Duration of therapy/rehabilitation
 
 
Data collected during walking:
 
 
Force plate data
 
Video monitoring data
 

Data analysis	
 
Comparative test between the primary outcome of three group
 
Wilcoxon sign rank test & a paired sample t test
 
Interclass correlation coefficient between those group
 
Mean difference and standard deviation between those group
 

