### **Summary:**

This study aims to collect and analyze spatiotemporal data from stroke patients using an in-house gait analysis setup. Each walking modality-overground, self-paced treadmill, and body-weight supported treadmill provides distinct advantages and challenges. Overground walking simulates natural conditions but lacks mechanical support; self-paced treadmill walking provides a controlled environment with adjustable speed; and body-weight supported treadmill walking reduces lower extremity pressure and the risk of falling. A locally made body weight support structure (BWSS) is used for fall prevention in hemiparetic patients during data collection. The BWSS includes: Hand winch system with locking mechanism, Double pulley system, An overhead harness, and A 10 ft Stainless steel wire (loading capacity=5 ton). For Overground, data collection is done using two force plates positioned in the middle of a linear pathway, an 8-camera video monitoring system, and AcqKnowledge software is used for data analysis. Data collection from the self-paced treadmill and body-weight supported treadmill also occur through the video monitoring system. Data collection will adhere to standard protocols to ensure safety and accuracy. Participants will walk along the pathway, and gait data will be recorded using the force plates and video system. By analyzing gait parameters such as step length, stride length, cadence, gait speed, and the duration of stance and swing phases, the study aims to identify which modality offers the most consistent and stable gait patterns, indicating improved motor control and coordination.

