### **Introduction:**

Stroke is the leading cause of disability worldwide, affecting the lives of millions of people. One of the most debilitating effects of stroke is impaired gait, which impairs mobility and independence [1]. It is especially prevalent in low- and middle-income countries such as Bangladesh. Stroke is the third leading cause of death from non-communicable diseases in Bangladesh, putting a significant burden on both individuals and the healthcare system. Stroke prevalence in Bangladesh is around 11.39 per thousand people, with higher rates in rural areas and among elderly males [2]. Gait abnormalities are experienced by about 80% of stroke survivors, and they can significantly impair their daily activities and overall quality of life [3]. The significant number of disability-adjusted life years (485 per 10,000 people) lost due to stroke severely impacts the nation's economy [4]. Despite the high occurrence of disability due to stroke in Bangladesh, there are significant limitations in analyzing the gait characteristics of stroke patients. Gait rehabilitation uses a variety of walking modalities, such as body weight supported treadmill walking, self-paced treadmill walking, and overground walking. Every modality has particular benefits and drawbacks. The most natural kind of gait training is provided by walking on terrain that closely resembles actual walking conditions. However, because of the unpredictable nature of the environment and the lack of

mechanical support, it can be challenging for stroke patients [5]. Self-paced treadmill walking provides a controlled environment in which the patient's speed can be adjusted based on their abilities, allowing for a consistent walking rhythm and feedback [6]. This modality is useful for strengthening gait patterns and increasing endurance. However, body weight supported treadmill walking allows the patient to partially offload their weight, which lessens the pressure on their lower extremities and improves safety by lowering the chance of falls [7]. Variability in gait parameters such as step length, stride length, cadence, gait speed, and the duration of the stance and swing phases is an important aspect of gait analysis. High variability in gait frequently indicates instability and inefficiency, which are undesirable outcomes in rehabilitation. Lower variability, on the other hand, indicates more consistent and stable gait patterns, implying improved motor control and coordination.

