## **Data collection procedure:**

Participants will be selected based on pre-determined inclusion criteria to ensure they fit for the study. Data will be collected through face-to-face interview using a pretested semi-structured questionnaire and informed verbal consent will be taken prior to interview. All the participants demographic information (age, weight, height, etc.) will be collected. Participants evaluated by Berg Balance test and Time Up & Go (TUG) test questionnaire form. All participant names have been properly defined to make sure confidentiality. After that the participants will be instructed to walk in their natural and comfortable manner. All participants will undergo a familiarization trial to get comfortable with the experimental setup and procedures. Then, participants will perform linear walking during two consecutive trials. Then take 2 minutes rest for treadmill walking after that again take 2 minutes rest for BWSTW. Data will be collected using a force plate and an 8-camera video monitoring system on all three walking modalities. The collected spatiotemporal data will be analyzed by statistical methods to identify differences among those modalities. Specific focus will be on key spatiotemporal parameters such as step length, stride length, cadence, gait speed, and the duration of the stance and swing phases use as important aspects of gait analysis

**Figure:** Flow chart of study plan

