# Case Report Form

**Project Title:** Spatiotemporal gait parameters of healthy and stroke patients during overground, self-paced treadmill, and body-weight supported treadmill walking.

Participant Information					
1.	Patient's name			Age	
2.	Patient ID			Gender	 Male  Female
3.	Address			Contact no.	
4.	Height (cm)		5. Weight (kg)		Date of Stroke
6.	Type of Stroke	 Ischemic  Hemorrhagic		7. BMI	
8.	Affected Side	 Right  Left			

Medical History					
9.	Hypertension	 Yes  No	10. Diabetes Mellitus	 Yes  No	
11.	Heart Disease	 Yes  No	12. Previous Strokes	 Yes  No	
13.	Peripheral Artery Disease	 Yes  No	14. Chronic Kidney Disease	 Yes  No	
15.	Smoking	 Yes  No	16. Alcohol Use	 Yes  No	
17.	BP		18. Heart Rate		Number of Previous Strokes

Gait Analysis Information					
19.	Date of Gait Analysis		20. Time Since Stroke (months)		
21.	Balance Test (Berg Balance Scale)	Score: _____/56	22. Muscle Strength (MRC Scale)	Right Leg: _____/5 Left Leg: _____/5	
23.	Spasticity (Modified Ashworth Scale)	Right Leg: _____/4 Left Leg: _____/4			

Gait Analysis Parameters					
24.	Walking Speed (m/s)		25. Cadence (steps/min)	_____	

26.	Stride Length (cm)	Right Leg: _____ Left Leg: _____	27. Step Length (cm)	Right Leg: _____ Left Leg: _____
28.	Gait Cycle Duration (s)	_____		
29.	Stance Phase (% of gait cycle)	Right Leg: _____ Left Leg: _____	30. Swing Phase (% of gait cycle)	Right Leg: _____ Left Leg: _____
31.	Double Support Time (s)	_____	32. Single Support Time (s)	_____
33.	Vertical GRF (N)	Paretic Leg: _____ Non- paretic Leg: _____	34. Anteroposterior GRF(N)	Paretic Leg: _____ Non- paretic Leg: _____
35.	Mediolateral GRF(N)		Paretic Leg: _____ non-paretic Leg: _____	

Observational Gait Analysis & Functional Outcome Measures					
36.	Initial Contact	 Heel	 Flat Foot	 Toe	

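### Mean vertical ground reaction force in newtons, compared with the body-weight supported condition, cannot separate the support from a change in gait

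*Protocol*

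**What the plan says.** Table 1 names gait velocity as the primary outcome and lists "Ground reaction force" last among the secondary outcomes, with no component, summary or normalisation. Its Data analysis row ties the comparative test to the primary outcome, but also has an entry tied to no outcome: "Mean difference and standard deviation between those group".

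The Case Report Form records force by paretic and non-paretic leg in items 33 to 35. Item 33 ("Vertical GRF (N") and item 34 ("Anteroposterior GRF(N") give the unit as newtons, and item 35 does the same for the mediolateral component. No field holds the support level or support force.

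The Introduction says that body-weight supported treadmill walking "allows the patient to partially offload their weight, which lessens the pressure on their lower extremities".

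The protocol describes force recording in two ways. The Data collection procedure says: "Data will be collected using a force plate and an 8-camera video monitoring system on all three walking modalities". The Summary in Annexure C says: "For Overground, data collection is done using two force plates positioned in the middle of a linear pathway", and for the other two modalities: "Data collection from the self-paced treadmill and body-weight supported treadmill also occur through the video monitoring system".

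**The concern.** A force plate under a supported patient registers only the load that the harness does not carry. Mean vertical force is then expected to be lower in that condition even if the patient walks exactly as before. The within-patient design removes differences in body weight between patients. It does not remove a shift that comes with one modality, because that shift coincides with the contrast of interest. With neither the support level nor the support force recorded, the planned data cannot recover the offset.

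At stake is the reading of one secondary outcome. A clear difference in vertical force could be reported as an effect of modality on gait when some or all of it is unloading. A change in the SD in newtons could likewise be taken as a sign of more, or less, consistent walking.

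**Working it through.** **The plan's own figure.** The only calculation in the protocol is for gait velocity: N = 2σ²(Z₁₋β + Z₁₋α/2)² / [d²(k − 1)], with σ = 0.3, d = 0.17, k = 3, 80% power and two-sided α = 0.05. This gives 2 × 0.09 × (0.84 + 1.96)² / (0.0289 × 2) = 1.4112 / 0.0578 = 24.4. The stated 24 is reproduced up to rounding, and 25 is planned after dropout. No figure is given for force, so what follows is illustration.

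**Assumptions not in the documents.** Body weight 65 kg (SD 12 kg), mean vertical force equal to one body weight, support s of 10% to 40%, and unchanged gait.

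**Shift in the mean.** Body weight is 65 × 9.81 = 638 N. Mean vertical force becomes 638 × (1 − s):

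| Support | Shift (N) | Mean under support (N) |
|---|---|---|
| 10% | 64 | 574 |
| 20% | 128 | 510 |
| 30% | 191 | 446 |
| 40% | 255 | 383 |

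**Chance that the shift alone is significant.** For a paired t test with n = 25 and two-sided α = 0.05, the noncentrality is (shift / SD of paired differences) × √25. For the smallest shift, 64 N:

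- SD 50 N: 64/50 × 5 = 6.4, power above 0.999
- SD 75 N: 64/75 × 5 = 4.27, power 0.98
- SD 100 N: 64/100 × 5 = 3.2, power 0.87

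Larger support gives higher power.

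**What happens to the SD.** Take a step-to-step SD of 3% of body weight (0.03 × 638 = 19 N), again an assumption.

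- *Support removes a constant force.* The SD stays at 19 N. The coefficient of variation rises from 3% to 3/(1 − s), that is 3.3% to 5.0%.
- *Force scales with the remaining load.* The SD becomes 19.1 × (1 − s), about 17 down to 11 N. The coefficient of variation stays at 3%.
- *The support force itself varies independently by 3% of body weight.* With force otherwise unscaled, the SD becomes √2 × 19.1 = 27 N.

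The between-patient SD behaves in the same way. It is 12 × 9.81 = 118 N without support. It falls to between 106 and 71 N if support is proportional to body weight, and stays at 118 N if the same force is removed from everyone.

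**Does the leg ratio escape?** Not across modalities. With illustrative leg forces of 550 and 650 N, the ratio is 550/650 = 0.85. Removing 128 N from each gives 422/522 = 0.81 with no change in gait. The ratio is usable within a modality, not as a contrast with the supported condition.

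**The case against.** The strongest objection is that Table 1 names no test of force between modalities. The comparative test is for gait velocity, and the Data collection procedure speaks of analysing spatiotemporal data. This stands in part: a formal force test is an inference. But force is a listed outcome of a between-modality study, and the mean difference and SD entry is restricted to no outcome, so on its face it covers force.

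Second, if the Summary is right, no treadmill force exists and there is nothing to compare. This also stands as a condition. On the Summary's version the contrast cannot be made. On the version in the Data collection procedure it is confounded. Neither gives an interpretable comparison of mean vertical force with the supported condition.

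Third, normalisation belongs in an analysis plan, and newtons on a form are only a recording unit. That would answer the point if the support force were captured, but the form has no field for it.

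Fourth, Annexure B allows an overhead harness for any patient afraid of falling, so some unloading outside the supported condition cannot be excluded. That is correct. It makes the offset less well defined but does not remove it.

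A reader might also infer that the equipment guarantees a smaller SD and so favours the study hypothesis. The documents do not support this. Subtracting a constant leaves the SD unchanged, and the hypothesis under Objectives concerns spatiotemporal parameters, which do not include force.

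**Conclusion.** The point holds for mean vertical force in newtons, on condition that force is recorded in the supported modality. Its difference from the other modalities then cannot separate support from a change in gait. Under the assumptions stated, the artefact is about 64 to 255 N, and its smallest value would be significant with probability from about 0.87 to over 0.99 at 25 pairs. Body weight, support level and paired SD are all assumed, so the size is indicative. The direction rests on the protocol's own account of what support does.

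The SD in newtons can move either way (about 11 to 27 N against 19 N in the illustration) and cannot be read as consistency in either direction.

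It would go too far to say that the force contrast measures only the equipment, since it mixes support with any real gait change. It would also go too far to extend the argument to all of ground reaction force, since anteroposterior and mediolateral force are not directly subtracted. The primary outcome, the spatiotemporal hypothesis and the sample size are untouched. This is a limited but worthwhile correction to one secondary outcome.

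**What to change.** - In Table 1, exclude vertical force in newtons from mean-difference and SD comparisons that involve the supported condition. Limit between-modality force comparison to unsupported modalities in which force is truly recorded.
- Report the paretic to non-paretic ratio from items 33 to 35 descriptively within each modality, not as a contrast with the supported condition.
- State that a lower absolute vertical force, or a different SD in newtons, under support is not evidence about gait consistency.
- Reconcile the Summary with the Data collection procedure on which modalities have force-plate data.

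The cost is wording in Table 1 and one of the two sections, plus a ratio derived from fields already on the form. One secondary contrast is lost, and it could not have been interpreted.

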## **Annexure – E**

### **Budget**

The total budget for the proposed study is Tk. 30,000/-. The budget of the project is provided below:

No	Description	Unit	Unit Cost (BDT)	Qty.	Cost (BDT)
1	Reimbursement -Travel Cost of participants	L.S.	1000	25	25,000
2	Miscellaneous Expenses	L.S.	4000	1	4000
3	Contingency (5%)	L.S	1000	1	1000
Total Cost					30,000

Grand Total: Tk. 30,000/-

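### Table 1 sets a three-modality comparison of gait velocity but names only two-condition tests, so primary-outcome family-wise error is about 5% or about 10-12.5% depending on an unstated gate

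*Protocol*

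**What the plan says.** The comparison is within person. Under Data collection procedure, participants walk overground, rest, walk on the treadmill, rest, and walk on the body-weight supported treadmill: "Data will be collected using a force plate and an 8-camera video monitoring system on all three walking modalities". The sample-size paragraph and Table 1 both make gait velocity primary.

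The Data analysis row of Table 1 lists, as separate bullets:

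- "Comparative test between the primary outcome of three group", with no test named;
- "Wilcoxon sign rank test" and "a paired sample t test", joined by an ampersand;
- an intraclass correlation, and mean differences with standard deviations, neither of which is a three-condition test.

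The sample-size paragraph (Phase-3-Extended Study) says that 24 people are "needed to satisfy the comparative studies between three groups, based on the statistical power of 80%, at a two-sided alpha level of 0.05". It adds: "The statistical formula (i) used for the comparative test". In that formula k "is the number of groups being compared".

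The protocol does not say which pairs are compared, which of the two named tests decides, or whether an overall result must come first.

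**The concern.** The protocol is not silent on method. It names tests, and they do not fit the comparison set one bullet above them: a paired t-test or a signed-rank test takes two conditions, and there are three. An analyst who applies the row as written would run the named tests pair by pair. With three pairs each at 0.05 and nothing in front of them, the primary outcome no longer carries the stated 5% error. The choice between t-test and Wilcoxon is also open, and a choice made after seeing the data adds to the error.

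At stake is whether a reported difference in gait velocity between modalities was obtained at about 5% false-positive risk or at about twice that.

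**Working it through.** **Inputs from the protocol.** Two-sided alpha 0.05, power 80%, mean difference d = 0.17, SD σ = 0.3, k = 3 (sample-size paragraph); 25 participants, each measured in three conditions. The correlations between modalities are not given, so a range is assumed.

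**The plan's own figure.** Formula (i): N = 2σ²(z₀.₈₀ + z₀.₉₇₅)² / [d²(k−1)] = 2 × 0.09 × (0.8416 + 1.9600)² / (0.0289 × 2) = 1.413 / 0.0578 = 24.44. The protocol reports 24, then 25 after dropout. The figure is reproduced apart from rounding. The protocol states no family-wise error rate, so there is none to reproduce.

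**Bounds for three tests at 0.05.** If independent, 1 − 0.95³ = 14.3%; by Bonferroni, 3 × 0.05 = 15%. Neither is the right figure here, because the three pairwise differences share data: any two of them determine the third. If two modalities are almost identical, two of the three tests nearly coincide and the limit is 1 − 0.95² = 9.75%.

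**Simulated family-wise error.** No true difference, n = 25, three conditions per person, 100,000 to 200,000 runs per main setting (Monte Carlo standard error about 0.1 percentage point):

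| Rule | Equal correlations | Unequal correlations or SDs |
|---|---|---|
| Three paired t-tests at 0.05, no gate | 12.2-12.5% | about 10-12% |
| Only the two BWST pairs, no gate | 9.1-9.2% | 6.4-9.8% |
| Three pairs, t-test or Wilcoxon may count, no gate | 14.1-14.3% | 13.3-13.5% with treadmill-pair correlation 0.8 or 0.9 |
| Repeated-measures ANOVA gate, uncorrected | 4.9-5.1% | up to 6.8% |
| ANOVA gate with Greenhouse-Geisser correction | 4.6% | 4.9-5.1% |
| Holm, no gate | 4.5% | not simulated |

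Over 55 random covariance patterns (20,000 runs each), three ungated t-tests gave a median of 11.6% (8.5-12.7%), and counting either test gave a median of 13.4% (9.7-14.4%).

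**Why a gate is enough with three conditions.** If all means are equal, a false claim needs a false overall test, which is held at 5%. If one mean differs from the other two, only one true-null pair is left, and it is tested at 0.05 (simulated false rejection 4.9%). If all three differ, no true-null pair is left.

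**Power of the alternatives.** Assume an SD of differences of 0.3, equal correlations, n = 25, and one modality differing from both others by 0.17. One unadjusted pair: noncentrality 0.17 / (0.3/√25) = 2.83, power 78%. Under the gate: overall test 82% (81% corrected), each real pair 73% (72% corrected). Under Holm: 64% per pair.

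These figures depend on the assumptions. If the three means are evenly spaced over 0.17, overall power is 69%. The protocol does not say whether 0.3 is the SD of differences or of a single condition. If it is the latter, the SD of differences is 0.3 × √(2(1−ρ)): 0.3 at ρ = 0.5, and 0.424 at ρ = 0. For SDs of differences of 0.2, 0.25, 0.35 and 0.424, overall power is 99%, 94%, 68% and 51%.

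**The case against.** The strongest reply is that this is ordinary SAP content. The name of the overall test, the rule for choosing between t-test and Wilcoxon, and any gate may all stand in an SAP that is not shown. The two bullets also make a coherent plan if read in order: an overall comparison, then pairs. The sample-size paragraph supports that reading by tying its comparative test to a formula with k groups. On that reading the error rate is about 5%.

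Much of this stands. A reader might infer that the plan has no three-way comparison, or that its error rate is certainly inflated, perhaps to 14-15%. The documents support neither. A three-group comparison is listed, the protocol nowhere says that ungated pairs are each tested at 0.05, and the 14-15% bounds ignore the dependence between pairs. The 10-12.5% also assumes that all three pairs are confirmatory. The hypothesis contrasts BWST with each of the other two, and does so on variability rather than mean velocity; for those two pairs the figure is about 9%.

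What the reply does not remove is the mismatch inside one table row. The only tests the protocol names cannot perform the comparison it sets, and an SAP would have to depart from the row or add to it to put that right.

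**Conclusion.** The point holds in a conditional form. Table 1 pairs a three-condition within-person comparison with two-condition tests and one undivided 0.05. Family-wise error for gait velocity at n = 25 is about 5% if the unnamed test is a valid overall test that gates the pairs, and about 10-12.5% if the named tests are applied to all three pairs without a gate. The two BWST pairs alone give about 9% (6-10%), and a free choice of test about 13-14%. All these figures rest on assumed correlations and on normal data.

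A reader might also infer that a gated analysis of 25 people secures the planned 80% power, or that it fails to. Neither follows: overall power is about 81-82% in one favourable configuration, 69% with evenly spaced means, and 51-99% over the SDs of differences examined.

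This should be corrected, but it is a matter of wording and prespecification rather than a flaw in the design.

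**What to change.** Reword the Data analysis row of Table 1, for example: gait velocity will be compared across the three modalities by repeated-measures ANOVA with Greenhouse-Geisser correction at two-sided alpha 0.05; only if this is significant will the three paired t-tests follow, each at 0.05; the Wilcoxon signed-rank test is a prespecified sensitivity analysis under the same gate. The correction matters, because an uncorrected gate can reach about 6.8% when sphericity fails.

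Holm-adjusted paired t-tests without a gate are a valid alternative. A mixed model with fixed modality and a covariance that lets the pairwise SDs differ is also possible, though not identical: the comparable unstructured test (Hotelling T²) has 79% overall power where the corrected ANOVA has about 81%. State one rule.

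Then restate the power for the rule chosen, with the SD of differences and the pattern of means it assumes.

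The cost is one reworded row and a restated power statement. The power statement is the harder part, because it needs an SD of differences that the protocol does not identify. Under the assumptions above, per-pair power falls from 78% to about 72-73% with the gate, or to 64% with Holm. Controlling the error rate needs no one beyond the 25 people budgeted in Annexure E under "Reimbursement -Travel Cost of participants"; whether 25 gives 80% power depends on the restated assumptions.
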